7.6. Treatment Compliance

All participants will receive study intervention administered by a qualified health care professional at the study site. Study intervention will be administered according to the instructions provided in the Study Operations Manual.

Accidental or intentional overdoses should be reported to the sponsor/designee promptly (see Section 9.4).

7.7. Prior and Concomitant Medications and Procedures

7.7.1. Prior Medications

The start and stop date, dose, unit, frequency, route of administration, and indication for all prior medications (taken within the 30 days prior to the Screening Visit) and nondrug therapies (eg, blood transfusions, oxygen supplementation, physical therapy, etc) received will be recorded.

In addition, all prior treatments administered for the disease/condition under study will be recorded with start and stop date, dose, unit, frequency and route of administration. The use of a collagenase at any point in time must be captured in the electronic case report form (eCRF).

7.7.2. Concomitant Medications

The start and stop date, dose, unit, frequency, route of administration, and indication for all concomitant medications taken from the Screening Visit through the EOS (Day 57) Visit, including oral and topical analgesics/anesthetics before study intervention injection, and nondrug therapies (eg, blood transfusions, oxygen supplementation, physical therapy, nutritional supplements, vitamins, vaccinations, etc) received will be recorded.

7.7.3. Prohibited Medications

The following medications are prohibited during the study:

- Opioids (eg, codeine, heroin, hydrocodone, hydromorphone, morphine, oxycodone) 2 weeks prior to the screening visit and during the study period.
- Anticoagulants (warfarin, heparin, direct thrombin inhibitors, Factor Xa inhibitors) and antiplatelet agents (aspirin > 150 mg/day and P2Y12 inhibitors, such as clopidogrel) from 7 days before the Day 1 Visit through the EOS (Day 57) Visit as

these medications can cause additional bruising. However, the use of aspirin ≤ 150 mg per day will be permitted.

- Injectable anesthetic use in or around the plantar nodule targeted for treatment is prohibited from the Day 1 Visit through the EOS (Day 57) Visit.
- Use of an investigational drug during the study

If any prohibited medication is taken during the study, all pertinent information will be recorded. The designated study medical monitor must be informed immediately so the sponsor may determine whether the participant can continue in the study.

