5.3. End of Study Definition

A participant is considered to have completed the study if the participant has completed the EOS (Day 57) Visit.

The end of study is defined as the completion of the final assessment for the last participant. All participants are expected to remain in the study until Day 57, regardless if they receive 1 or 2 treatments.

The study completion date is defined as date the final participant was examined or received an intervention for purposes of final collection of data for the primary and secondary outcome measures and adverse events (e.g., last participant's last visit or 28-day follow-up Safety Visit), as shown in the Schedule of Assessments (Section 2.3). This study completion date applies whether the study concluded according to the pre-specified protocol or was terminated.

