8. DISCONTINUATION FROM STUDY INTERVENTION AND PARTICIPANT WITHDRAWAL

8.1. Discontinuation of Study Intervention or from the Study

In rare instances, it may be necessary for a participant to be permanently discontinued from study intervention by the investigator or the sponsor for safety, behavioral, or compliance reasons. Participants who request to discontinue from the study intervention or discontinue from the study prior to the Day 57 visit will be encouraged to complete the remaining study visits and evaluations and provide any additional follow-up information as required by the study. Participants who discontinue from the study intervention and do not agree to remain in the study for follow-up until Day 57, will be requested to complete an ET visit and if applicable the 28-day post-treatment Safety Follow-up Visit (or phone call if a visit is not possible) to determine the status of any ongoing AEs/SAEs or the occurrence of any new AEs/SAEs. The date of and reason for discontinuation of study intervention will be recorded.

Discontinuation of study intervention for abnormal liver function will be considered by the investigator when a participant meets one of the conditions outlined in Section [11.5](#).

If a clinically significant finding is identified after the start of study intervention, the investigator or a qualified designee will discuss with the sponsor to determine if the participant can continue in the study and if any change in management is needed.

Participants who discontinue study intervention will not be replaced according to the discretion of the sponsor and discussion as needed with investigator.

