9. STUDY ASSESSMENTS AND PROCEDURES

Study procedures and their timing are summarized in the Schedule of Assessments (Section 2.3). Adherence to the study design requirements, including those specified in the Schedule of Assessments, is essential and required for study conduct. Protocol waivers or exemptions are not allowed. Activities outlined in the Study Operations Manual must be followed or a protocol deviation will result.

Urgent safety concerns should be discussed with the sponsor immediately upon occurrence or awareness to determine if the participant should continue study intervention and/or be discontinued from the study.

All screening evaluations must be completed and reviewed to confirm that potential participants meet all eligibility criteria. The investigator will maintain a screening log to record details of all participants screened and to confirm eligibility or record reasons for screen failure, as applicable.

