10.3.1.1. Primary Analysis

10.3.1.1.1. Primary Estimand

Primary Endpoint:

The difference between EN3835 and placebo in the mean change from Baseline (Day 1) to Day 57 on the foot pain subscale (total score on 9 items) of the FFI ranging from 0 (“None”) to 4 (“Extreme”).

The primary estimand is defined as follows:

In participants with plantar fibromatosis, what is the difference in mean change from baseline (Day 1) to Day 57 in foot pain score (as measured with the FFI pain subscale) between EN3835 and placebo regardless of discontinuation of study intervention?

The primary estimand includes the following components:

- Treatment of interest: The randomized study intervention (EN3835 or placebo)
- **Target Population:** Adult participants with plantar fibromatosis who are included in the ITT Population.
- **Variable (Endpoint) of interest:** Change from Baseline (Day 1) to Day 57 in FFI pain subscale score.
- **Treatments being compared:** The mean change from Baseline (Day 1) to Day 57 in FFI pain subscale score will be compared between EN3835 and placebo.
- **Intercurrent Event:** The treatment policy strategy will be adopted for primary analysis.
 - Any new or change in concomitant treatment will not be adjusted for in the primary analysis.
 - Early discontinuation from the study or loss to follow up: If participants do not have a FFI pain subscale score at Day 57, the missing values will be imputed before the analysis using a multiple imputation washout model. In multiple imputation washout model, all participants who are randomized and have a baseline assessment will be considered.
- **Population Level-Summary measure:** Least square mean (LSM) estimates for treatment difference between EN3835 and placebo.

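### Three protocol sections let a sponsor or investigator decision end study participation, not only study intervention, which does not fit a treatment-policy estimand that needs the Day 57 score

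*Protocol*

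**What the plan says.** Three places put continuation in the study up for decision.

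- **Prohibited medication** (Protocol 7.7.3, repeated in SAP 3.12.3): "The designated study medical monitor must be informed immediately so the sponsor may determine whether the participant can continue in the study".
- **Clinically significant finding** (Protocol 8.1): "the investigator or a qualified designee will discuss with the sponsor to determine if the participant can continue in the study".
- **Urgent safety concern** (Protocol 9): a discussion with the sponsor "to determine if the participant should continue study intervention and/or be discontinued from the study".

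The estimand sections and the follow-up rules point the other way.

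- **Primary estimand** (Protocol 10.3.1.1.1): "The treatment policy strategy will be adopted for primary analysis", and "Any new or change in concomitant treatment will not be adjusted for in the primary analysis". Key secondary estimands 1 to 3 use the same strategy.
- **End of study** (Protocol 5.3): "All participants are expected to remain in the study until Day 57, regardless if they receive 1 or 2 treatments".
- **Encouragement to stay.** Protocol 8.1 addresses participants who themselves ask to stop. Protocol 10.3.1.1.2, SAP 4.1 and footnote s of the Schedule of Assessments are wider and include people who have discontinued from the study.

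A Day 57 score that is missing because the participant left the study is imputed with a washout model. SAP 6.3.1 says this model assumes an outcome like that of comparable placebo participants. SAP 6.3.2 uses similar methods for the pain and difficulty combined score and for hardness. On the Clinician Global Impression of Change (CGIC), early leavers count as non-responders (Protocol 10.3.1.2.2, SAP 4.8.1).

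**The concern.** A treatment-policy estimand asks what happened by Day 57 whether or not the participant took another drug or stopped treatment. It can be estimated without modelling only if people are followed after the event. An opioid taken for foot pain is both a change in concomitant treatment, after which section 10 wants the score, and a prohibited medication, after which 7.7.3 allows participation to be ended.

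Study intervention is given only on Day 1 and, where applicable, Day 29. After the second visit, ending participation can no longer change exposure; what it does change is whether Day 57 is observed.

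The triggers may be related to outcome: analgesic use can reflect worse pain, and a clinical finding can reflect a local reaction. With case-by-case discretion on top, any missing data created this way could be informative. What would be lost is an observed value of exactly the kind the estimand is defined on, replaced by an assumption.

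**Working it through.** **1. The plan's own figure.** Inputs from Protocol 10.1 and SAP 3.5: difference 5.0, SD 10, two-sided alpha 0.05, power 85%, dropout 15%.

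- Normal approximation: n = 2 × (1.960 + 1.036)² × 10² / 5.0² = 71.8, so 72 per arm.
- Two-sample t-test: 72.8, so 73 per arm (power 85.1%). This matches the plan.
- Dropout: 146 / 0.85 = 171.8, so 172 in total and 86 per arm. This matches.

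The sample size reproduces, and nothing below depends on an error in it.

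**2. What removal does to the primary difference.** Let q be the share of each arm removed and d the true difference between arms at Day 57 among those people, had they been followed. Assume that imputation gives the removed participants in both arms the same placebo-like mean, and that the removed placebo participants would have averaged that same mean.

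- Followed to Day 57: D = 5.0 × (1 − q) + q × d
- Removed and imputed: D = 5.0 × (1 − q) + q × 0
- Change caused by removal: −q × d

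Neither document gives q or d, so both are assumptions.

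| q | about n of 86 | D if removed | D if followed, d = 5 | D if followed, d = 0 |
|---|---|---|---|---|
| 1% | 1 | 4.95 | 5.00 | 4.95 |
| 3% | 3 | 4.85 | 5.00 | 4.85 |
| 5% | 4 | 4.75 | 5.00 | 4.75 |

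At q = 5% the followed value is 4.75 + 0.05 × 2.5 = 4.88 (rounded) if d = 2.5, and 4.75 − 0.05 × 2.5 = 4.62 (rounded) if d = −2.5. Removal therefore lowers the estimate when d is positive, raises it when d is negative, and leaves it alone when d is 0.

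**3. Scale.** The standard error at 86 per arm is 10 × √(2/86) = 1.52. The largest shift in the table, 0.25 points, is 0.25 / 1.52 = 0.16 of a standard error. Power at 86 per arm, by the normal approximation and ignoring covariate gain and between-imputation variance, is 90.6% at D = 5.0, 90.1% at 4.95 and 87.6% at 4.75.

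**4. CGIC.** One participant reclassified as a non-responder is 1/86 = 1.2 percentage points of an arm. That is an upper bound per removal: it requires that the person would have been a responder, and removals in the two arms partly cancel.

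**5. The wording, side by side.** Elsewhere the protocol already separates the two decisions. The first sentence of 8.1 describes imposed discontinuation for safety, behavioral or compliance reasons as being from study intervention. Sections 9.2.6 and 9.3.5 stop dosing in pregnancy but let the participant stay in the study. Section 11.5 withdraws confirmed Hy's Law cases from study intervention. Section 8.2 treats withdrawal from the study as withdrawal of consent. Against that pattern, 7.7.3 and the clinical-finding sentence of 8.1 mention only the study, and section 9 names both decisions but keeps removal from the study as an option.

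**The case against.** The strongest reply is that nothing here requires removal. 7.7.3 gives the sponsor a choice and does not say that Day 57 data collection stops. Section 10.3.1.1.2, SAP 4.1 and footnote s encourage visits even after discontinuation from the study, and 10.3.1.1.2 does so because the estimand needs Day 57. On this reading follow-up is the default. Most of this stands: a score is lost only when the discretion is used and the participant is not followed. What remains is that encouragement to attend cannot be squared with a decision that the participant may not continue. The early termination visit collects the Foot Function Index at exit, which is not a Day 57 value.

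A second reply is that the estimand foresees missing Day 57 scores, imputes them, and is backed by a repeated-measures analysis of observed data and a tipping-point analysis. That is true, although SAP 6.3.1 drops the tipping-point analysis when the primary result is not significant. These methods examine the consequences of missing scores; they do not recover scores that could have been collected.

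Three stronger readings are tempting, and the documents do not support them.

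- **That the plan removes everyone who takes a prohibited drug.** It only permits a decision.
- **That the bias has a known direction or size.** A shift of 0.05 points per 1% removed assumes the full 5.0-point benefit in people who may have needed an opioid. The washout steps in SAP 7.6.1.2 are redacted, so one cannot see whether a placebo participant's own Day 15, 29 and 43 scores inform the imputed value.
- **That nobody may ever be taken out of the study on safety grounds.** Section 9 leaves room for urgent safety decisions, and prohibited medication before Day 29 also bears on whether a second dose is given. The point concerns data collection only.

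**Conclusion.** The point holds as a mismatch between sections with a conditional consequence. Sections 7.7.3, 8.1 and 9 of the protocol, and SAP 3.12.3, allow a decision that ends study participation, while the estimand, section 5.3 and the follow-up text all assume continued observation. If the discretion is exercised and follow-up stops, an observed value gives way to a placebo-like value for the Foot Function Index scores and hardness, or to a non-response on the CGIC.

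The size is unknown, because no rate of prohibited-medication use or of imposed exits is given, and it is probably small. Under the assumed 1% to 5% removal, the shift in the primary difference ranges from nothing (no post-event difference) to 0.05 to 0.25 points (full benefit retained), and it reverses if the post-event difference favours placebo. The change is worth making because it is cheap and protects the stated estimand, not because the result is shown to be at risk.

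**What to change.** Reconcile Protocol 7.7.3, 8.1 and 9 and SAP 3.12.3 with Protocol 5.3, 10.3.1.1.1 and 10.3.1.1.2 and SAP 4.1, in two statements:

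1. The decisions described in these sections concern study intervention.
2. A participant whose intervention is stopped for prohibited medication, a clinical finding, an adverse event or non-compliance is still asked to attend the scheduled visits. Day 57 efficacy and safety data are collected unless consent is withdrawn, the participant is lost to follow-up or dies, or an assessment cannot safely be done.

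How clinical and safety decisions are reached, and by whom, stays as it is.

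The cost is wording in three protocol sections and one SAP section. No visits are added, because they are already in the Schedule of Assessments. The downside is that sites keep following a few non-adherent participants, which treatment policy calls for in any case.

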7.8. COVID-19-Related Protocol Deviations

All study assessments conducted outside of the allowed windows outlined in the Schedule of Assessments due to a COVID-19 interruption will be documented as a protocol deviation. COVID-19 will be recorded as the reason for these out-of-window assessments.

8. DISCONTINUATION FROM STUDY INTERVENTION AND PARTICIPANT WITHDRAWAL

8.1. Discontinuation of Study Intervention or from the Study

In rare instances, it may be necessary for a participant to be permanently discontinued from study intervention by the investigator or the sponsor for safety, behavioral, or compliance reasons. Participants who request to discontinue from the study intervention or discontinue from the study prior to the Day 57 visit will be encouraged to complete the remaining study visits and evaluations and provide any additional follow-up information as required by the study. Participants who discontinue from the study intervention and do not agree to remain in the study for follow-up until Day 57, will be requested to complete an ET visit and if applicable the 28-day post-treatment Safety Follow-up Visit (or phone call if a visit is not possible) to determine the status of any ongoing AEs/SAEs or the occurrence of any new AEs/SAEs. The date of and reason for discontinuation of study intervention will be recorded.

Discontinuation of study intervention for abnormal liver function will be considered by the investigator when a participant meets one of the conditions outlined in Section [11.5](#).

If a clinically significant finding is identified after the start of study intervention, the investigator or a qualified designee will discuss with the sponsor to determine if the participant can continue in the study and if any change in management is needed.

Participants who discontinue study intervention will not be replaced according to the discretion of the sponsor and discussion as needed with investigator.

8.2. Participant Withdrawal from the Study

A participant may withdraw from the study (withdraw consent) at any time at his/her own request.

- At the time of withdrawing from the study, if possible, an ET visit should be conducted, as shown in the Schedule of Assessments
- The participant will be permanently discontinued from the study intervention, and the study, at the time of withdrawal of consent.
- If the participant withdraws consent for the sponsor may retain and continue to use any data collected before the withdrawal of consent.
- If a participant withdraws from the study, he/she may request destruction of any samples taken and not tested, and the investigator must document this in the site study records.

The date a participant withdraws and the reason for withdrawal will be recorded in the source documentation and the electronic case report form (eCRF). When a participant withdraws consent and does not agree to an ET visit, then no procedures are required.

8.3. Lost to Follow-up

A participant will be considered lost to follow-up if the participant repeatedly fails to return for scheduled visits and is unable to be contacted by the study site.

The following actions must be taken if a participant fails to return for a required study visit:

- The site must attempt to contact the participant and reschedule the missed visit as soon as possible and counsel the participant on the importance of maintaining the assigned visit schedule and to ascertain whether or not the participant wishes to and/or should continue in the study.
- Before a participant is deemed lost to follow-up, the investigator or designee must make every effort to regain contact with the participant (where possible, 3 telephone calls, and if necessary, a certified letter to the participant's last known mailing address; or local equivalent methods). These attempts will be documented.
- Should the participant continue to be unreachable, the participant will be considered to have withdrawn from the study.

Participants who have been lost to follow-up may be replaced according to the discretion of the sponsor.

9. STUDY ASSESSMENTS AND PROCEDURES

Study procedures and their timing are summarized in the Schedule of Assessments (Section 2.3). Adherence to the study design requirements, including those specified in the Schedule of Assessments, is essential and required for study conduct. Protocol waivers or exemptions are not allowed. Activities outlined in the Study Operations Manual must be followed or a protocol deviation will result.

Urgent safety concerns should be discussed with the sponsor immediately upon occurrence or awareness to determine if the participant should continue study intervention and/or be discontinued from the study.

All screening evaluations must be completed and reviewed to confirm that potential participants meet all eligibility criteria. The investigator will maintain a screening log to record details of all participants screened and to confirm eligibility or record reasons for screen failure, as applicable.

9.1. Efficacy Assessments

Examination and evaluation of the selected nodule(s) will be performed at the time points specified in the Schedule of Assessments. A general description of each of these assessments follows. Specific instructions and questionnaires/forms (where appropriate) will be provided in the Study Operations Manual.

9.1.1. Nodule Assessments

9.1.1.1. Anatomical Representation of Nodule Location

At Screening, Days 1, 29, and 57 Visits, the investigator will complete a graphic representation of the foot/feet and the location(s) of the nodule(s) treated.

Additional information is provided in the Study Operations Manual.

9.1.1.2. Consistency of the Selected Nodule

At the time points listed in the Schedule of Assessments, the investigator or qualified designee will palpate the selected nodule, determine the consistency of the nodule, and classify the nodule. For the first treatment, only hard, firm throughout, or moderately firm, palpable fibrous nodules will be treated. For the second treatment, nodules previously treated on Day 1 that remain palpable and are either hard, firm throughout, moderately firm, or soft) are eligible for Treatment 2. All efforts should be made to ensure the same investigator is performing these assessments for each participant. The nodule consistency scale is classified as,

4: Hard

3: Firm Throughout

2: Moderately Firm

1: Soft

0: Non-palpable.

Additional information on the classification of the nodule is provided in the Study Operations Manual.

9.1.1.3. Caliper Measurements of the Selected Module

At the time points listed in the Schedule of Assessments, the investigator or qualified designee will use a surgical marker to outline the circumference of the selected nodule.

After the nodule has been marked, the investigator or qualified designee will use handheld calipers to measure the length and width of the selected nodule, and nodule measurements will be recorded.

Gross observations will be solicited from the investigator from the investigator at each time of examination.

Additional information is provided in the Study Operations Manual.

